### 14.3.4 Determination of Subjects/Data for Analysis

Enrolled subjects who have Reveal LINQ™ device successfully inserted and have either the LINQ™ HF or ALLEViate-HF investigational RAMware successfully downloaded to the device and who have completed a first successful CareLink transmission.

## 14.4 Sample Size Determination

There are no sample size requirements as this is an observational study with no hypothesis for the study objective. A sample size of up to 100 enrolled subjects was selected assuming sufficient data can be collected from this cohort to explore the relationship between changes in LINQ™ derived data with COPD events.

According to a review by Seemungal et al., the annual rates of COPD exacerbations were estimated to be as low as 0.5 to a high of 3.5 exacerbations per patient from several studies, and hospitalization rates ranged from as low as 0.09 to 2.4 per patient per year. This study requires that a subject should have 2 COPD exacerbations within the previous 12 months as one of the inclusion criteria. Assuming the COPD exacerbation rate remains as 2 COPD exacerbations per patient year after subjects are enrolled, a group of 60 enrolled subjects being followed up for 12 months after successful insertion of Reveal LINQ™ device and download of the investigational RAMware would expect to have 120 COPD exacerbations. Assuming 50% of the COPD exacerbations would meet the study definition of “COPD event”, a total of 60 COPD events would be expected.

## 14.5 Minimization of Bias

Selection of subjects, treatment of subjects, and evaluation of study data are potential sources of bias. Methods incorporated in the study design to minimize potential bias include (but are not limited to):

- Subjects will undergo screening to confirm eligibility with defined inclusion/exclusion criteria prior to enrollment.
- All sites will use the same version of the Clinical Investigation Plan and electronic case report forms (eCRFs).
- All investigational site personnel and Medtronic personnel will be trained using standardized training materials.
- Monitoring visits will be conducted for adherence to the CIP and verification of source data.
- An independent Event Adjudication Committee (EAC) will be used to review and adjudicate at a minimum, all Pulmonary related AEs and all AEs with a fatal outcome.
- A statistical analysis plan will be developed prior to analyzing data. The plan will document all pre-specified analyses and analysis methods.

In summary, potential sources of bias that may be encountered in this clinical study have been considered and minimized by careful study design.

## 14.6 Missing data

Missing data will not be imputed. An adjudicated COPD event will be considered in the analysis to assess changes in LINQ™ derived data if it has Reveal LINQ™ data before and after the event onset date.

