**Medtronic Business Restricted**

**CONFIDENTIAL**

056-F275 Rev E Clinical Investigation Plan Template

	
Scheduled In-office Follow-up Visit (optional): Baseline Measurements, medication assessment, device interrogation (save to media via USB) (pre and post visit procedures), spirometry tests with Holter, patient assistant activity, Chest x-ray, adverse events, device deficiencies, study deviations
 
Study Exit Visit: Reason for exit, removal of LINQ HF or ALLEViate-HF RAMware from LINQ™ device, device interrogation (save to media via USB), opting out of the subject diary, SGRQ, Medication assessment, labs, adverse events, device deficiencies, study deviations
 
Additionally, up to 20 subjects will be asked to place an EMFIT monitor under their bed for the length of their study participation, with no more than 10 subjects per site. Furthermore, LINQ™ device data will be collected bi-weekly via CareLink manual transmissions as well as system modifications and subject deaths will be collected.

Safety Assessments	All LINQ™ system and procedure-related adverse events (AEs), all serious adverse events (SAEs), all Pulmonary related AEs and all Cardiovascular related AEs will be collected throughout the study duration of a subject's participation in the study, beginning at the time of informed consent. An Event Adjudication Committee (EAC) will conduct a medical review of all adverse events classified by the investigator or Medtronic as Pulmonary related and all AEs with a fatal outcome. The EAC will consist of non-Medtronic employed physicians that are not participating investigators for the study.
Statistics	Since the study will be exploratory in nature and the study objectives are descriptive, no clinical endpoints will be developed. LINQ™ derived data will be summarized using descriptive statistics. Their relationship to COPD events (per EAC adjudication) will be evaluated by looking at the data before and after the occurrence of COPD events to identify potential patterns and signals.

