## 4.2 Purpose

The ability to predict which patients will subsequently have an exacerbation for COPD using the traditional evaluation measures such as physical signs and symptoms is limited. Medical interventional methods currently may not identify patients early enough to prevent an exacerbation. To help reduce these exacerbations and improve disease management, sensors in a minimally invasive device can be used to identify factors that are associated with exacerbations. Thus, a solution to continuously monitor COPD patients at risk for acute exacerbations (GOLD stage C/D) in an ambulatory fashion to predict symptom worsening and provide timely remote intervention to prevent hospitalizations is an unmet clinical and economic need. Using sensors in a minimally invasive device like LINQ™ to sense, predict and prevent COPD hospitalizations is the overarching objective of this project. As a first step, the LINQ-COPD study aims to collect sensor data to characterize the changes in these sensor data prior to COPD hospitalizations with the aim to develop a prediction algorithm that can identify when patients are at risk and may benefit from a remote intervention.

Prior studies have shown implantable device-measured diagnostics like intra-thoracic impedance, AF burden, heart rate metrics, respiration, and patient activity metrics can be used individually or in a

combined fashion to identify when patients are at risk for certain events. We hypothesize that these measurements made in the subcutaneous thoracic space may be sensitive enough to detect physiological changes associated with COPD.

The use of implantable device features such as the OptiVol™ impedance algorithm is clinically useful in monitoring thoracic fluid status for pacemaker or ICDs and may be measured in the subcutaneous space. The Monitoring in Dialysis (MiD) study was conducted in renal failure patients implanted with a Reveal LINQ™ insertable cardiac monitor. The results indicated impedance trends upwards with fluid removal during dialysis sessions and downwards between dialysis sessions. Therefore, the preliminary data show that continuous impedance monitoring has a direct inverse relationship to patient thoracic fluid status in both a detailed analysis and long-term trending analysis.

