**Figure 6: Patient Assistant**

## 7.1.7 MyCareLink ® Home Monitor

The MyCareLink® Home Monitor is a device that enables the device diagnostic data (which includes ECG data) to be transmitted directly from the implanted Reveal LINQ™ device to the Medtronic CareLink® Network for review by the physician. The additional data that is stored in the device by the investigational RAMware is also transmitted during a manual CareLink transmission but will not be available for review by site and or physician.

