## 10.11 Bi-Weekly CareLink Transmissions

Subjects will be provided with a MyCareLink Patient Monitor and enrolled in the Medtronic CareLink network, and will be instructed on how to set up their monitor to support automatic nightly transmission of their device data. In addition, subjects are required to perform a manual device transmission bi-weekly (every 14 days) from the time they are enrolled in the study until they are exited from the study. This transmission is critical as data collected by the investigational RAMware will be overwritten if not manually transmitted within 32 days.

As described above, the subjects are required to complete a bi-weekly transmission. A report will be made available to the site identifying subjects who have missed their manual transmission.

A monthly study deviation will be required if 2 straight bi-weekly transmissions are missed, unless a device interrogation file for an interrogation occurring within the required timeframe is provided to Medtronic.

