## 14.3 Primary Objective

The primary objective is to characterize Reveal LINQ™ derived data from patients with COPD by assessing the relationship between changes in LINQ™ derived data with subsequent COPD events.

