### 14.3.3 Analysis Methods

Data from multiple study components will be collected in this study, of which the Reveal LINQ™ HF derived data is of the most interest. This includes subcutaneous electrocardiogram, impedance, temperature, accelerometer and patient activity measurements.

Descriptive statistics such as mean and standard deviation for continuous variables and count and proportion for categorical variables will be used to summarize the derived data from Reveal LINQ™ HF. The relationship between changes in LINQ™ derived data and COPD events per EAC adjudication will be evaluated. Specifically, for each subject that has experienced at least one COPD event per EAC adjudication, the average daily measurements of LINQ™ derived data before and after a COPD event will be plotted to identify patterns and signals related to the occurrence of the COPD event.

Baseline data such as demographics, medical history, physical exam (heart rate, blood pressure, weight, spirometry assessment, etc.), and blood measurements (Creatinine, BNP, NT-pro BNP, White Blood Cells and Eosinophils) will also be summarized using descriptive statistics.

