7.4 Handling of Missing, Unused, and Spurious Data and Dropouts

Missing data will not be imputed. An adjudicated COPD event will be considered in the analysis to assess changes in LINQ™ derived data if it has device data before and after the event onset date.

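### Minor: Protocol 14.6 and SAP 7.4 make an event's place in the pre-onset display depend on data after onset, and no count of events lost this way is planned.

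*Protocol*

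**What the plan says.** Protocol 14.6 rules out imputation and takes an adjudicated COPD event into the analysis of LINQ changes "if it has Reveal LINQ™ data before and after the event onset date". SAP 7.4 repeats this with slightly different words: "if it has device data before and after the event onset date". Both sentences say 'if' rather than 'only if', but as the data rule in a missing-data section they are naturally read as a condition of entry.

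The primary objective (Protocol 14.3, SAP 7.9) is to characterise the data by "assessing the relationship between changes in LINQ™ derived data with subsequent COPD events". Protocol 4.2 describes the study as a first step that aims to "characterize the changes in these sensor data prior to COPD hospitalizations", with a prediction algorithm in view.

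The planned method covers both sides of the event. The Statistics row of the Protocol synopsis speaks of "looking at the data before and after the occurrence of COPD events to identify potential patterns and signals", and Protocol 14.3.3 and SAP 7.9.3 state that "the average daily measurements of LINQ™ derived data before and after a COPD event will be plotted". None of these places gives a number of days.

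On reporting, SAP 7.1.1 plans a STROBE diagram of visits, deaths and exits, SAP 7.1.2 a deviation summary, and SAP 7.10 an adverse event listing. None of them shows which adjudicated events failed the data rule.

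**The concern.** The objective looks forward from a sensor change to a later event. For that purpose the informative data lie before onset. An event with a complete run-up and nothing recorded afterwards carries the information wanted, yet the rule leaves it out. The reason for leaving it out is something that happened after onset, so entry depends in part on the outcome of the event.

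The events exposed to this are those that stop the data stream: a rapid death, an exit, or no further transmission. These may include severe events, and hospitalised exacerbations are the ones that Protocol 4.2 has in mind. Without a count by reason, a reader of the final report cannot tell how many events were left out or why. The study has no hypothesis, so what is at stake is how selected and how readable the display is, not a test result.

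**Working it through.** **1. The plan's own event projection.** Protocol 14.4 and SAP 6 assume 60 subjects, 12 months, 2 exacerbations per patient-year and 50% meeting the event definition.

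- 60 × 2 × 1 = 120 exacerbations
- 120 × 0.5 = 60 COPD events

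This reproduces the stated 60. The projection makes no allowance for events that fail the data rule.

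**2. How large could one source of loss be?** The documents give no exclusion rate, so only an illustration is possible. Protocol 4.1 says that about 11% of patients admitted for exacerbation die within 90 days, half of them in hospital, and that 46% of COPD patients had an exacerbation in the previous year while 19% needed hospitalisation.

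- In-hospital deaths per admission: 0.11 × 0.5 = 0.055
- Share of events that are admissions (assumed): 19%; or 19/46 = 41%; or all

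| Assumed admission share | Admissions among 60 events | In-hospital deaths (× 0.055) | Share of 60 |
|---|---|---|---|
| 19% | 11.4 | 0.6 | 1.0% |
| 41% | 24.8 | 1.4 | 2.3% |
| 100% | 60 | 3.3 | 5.5% |

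The 19% and 46% describe patients, not events, so the first two shares are assumptions. The table counts deaths, not exclusions: a death that leaves any post-onset data still meets the rule. Exits and missed transmissions are not in the table, because the documents give no rate for them.

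**3. What a recovered event would contribute.** Protocol 10.11 sets manual uploads every 14 days. Suppose uploads were on schedule, none followed onset, and onset falls uniformly in the 14-day cycle. The gap x between last upload and onset is then uniform on 0 to 14 days.

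- Mean gap: 14/2 = 7 days
- Mean share of the last W days held: mean of max(W − x, 0), divided by W
- W = 7: 1.75/7 = 25%
- W = 14: 7/14 = 50%
- W = 30: 23/30 = 77%

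If the latest scheduled upload was missed, the gap runs from 14 to 28 days and none of the last 14 days is held. The documents give no rate of missed uploads, so this case carries no probability. It does show that admitting an event on a single day of data in a long window would let in events with nothing close to onset. Showing the number of events on each day makes that visible.

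**The case against.** The rule matches the analysis chosen. The synopsis, Protocol 14.3.3 and SAP 7.9.3 all describe a before-and-after comparison, and an event seen on one side only cannot supply it. In an exploratory study, keeping the same events on both sides is a defensible choice. This stands for the post-event part; it does not explain why the pre-event part should need later data.

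The plan also has routes that recover data. Protocol 12.6 asks for device interrogation after a death if available, 10.23.1 for interrogation at exit before the RAMware is removed, and 10.17 for interrogation at a system modification. Under 10.11 an interrogation file can stand in for missed transmissions. RAMware data are held for 32 days, so a prompt interrogation could restore both the run-up and some post-onset data. This also stands, and is why the loss is likely to be small. These routes are not certain to succeed, and no count is planned that would show whether they did.

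Three stronger readings are tempting:

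- A reader might infer that nightly standard data alone satisfy the rule. SAP 7.4 refers to device data generally; Protocol 10.11 has subjects set up their monitor "to support automatic nightly transmission of their device data", whereas Protocol 7.1.7 says "The additional data that is stored in the device by the investigational RAMware is also transmitted during a manual CareLink transmission". But Protocol 14.3.3 and SAP 7.9.3 name the sensor data of interest, and an event with none of them has nothing to plot. This is loose wording.
- A reader might see a contradiction with Protocol 14.3.2 and SAP 7.9.2, which include all of a subject's events. Those sentences deal with subjects who have several events; at most a cross-reference is missing.
- A reader might conclude that the rule removes the most severe events and biases the display. The documents show that this could happen, not that it will or to what extent.

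**Conclusion.** The point holds as a minor one. As written, an adjudicated event with usable pre-onset data can be left out solely because nothing was recorded after onset, although the objective concerns changes before the event, and no count of such events is planned. The absence of a stated window is missing detail rather than an error.

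The loss is probably small and the documents do not allow it to be quantified. The 0.6 to 1.4 of 60 events is an illustration under assumed admission shares of 19% to 41%. It is not an upper limit, since the figure is 3.3 if every event is an admission. Nor is it an estimate of exclusions, since some of those deaths would leave post-onset data. The average of 7 missing run-up days for a recovered event rests on uploads being on schedule and onset being uniform in the 14-day cycle. No test or error rate is affected.

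**What to change.** Add to SAP 7.4, and align Protocol 14.6 at its next revision:

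> LINQ sensor data after the onset date are required only for the post-event part of the display. An event with LINQ sensor data in the pre-onset window plotted is included in the pre-event part. The number of events contributing on each day relative to onset is shown, and the number of adjudicated events excluded from each part is reported by reason.

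The sponsor should fix the window and any minimum coverage before viewing event data.

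The cost is a few sentences and one small table from data already collected. Protocol 14.1 requires an amendment only when a principal feature changes, and Protocol 16.6 requires sponsor and ethics approval at each center for a revised protocol, so the SAP is the place to start. The downside is that event counts will differ slightly between the two halves of the plot, and recovered events without a later upload will lack some of the final pre-onset days.

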## 14.7 Additional Considerations Due to COVID-19

- Subject follow-up visits.

Follow-up visits every three months post device insertion will be done by telephone or in-person if desired. The flexibility in the way to complete these visits will allow subjects to continue to be followed in the study as well as to follow local COVID-19 guidelines.

- COPD exacerbation rate.

A patient with COVID-19 may be at higher risk of a COPD exacerbation event. At the same time there could be underreporting of COPD exacerbation events compared to literature. Therefore, the impact of COVID-19 on the COPD exacerbation rate is unknown.

- COPD event outcome.

Under potentially limited care resources of sites due to COVID-19, subjects with COPD may experience delayed treatment that could also increase the subject's risk of worse outcomes. In addition, subjects with COPD may experience worse/poorer event outcomes if also infected by COVID-19.

## 15. Ethics

---

### 15.1 Statement(s) of Compliance

The LINQ™ for COPD Study will be conducted according to the Declaration of Helsinki, Version 2013, Clinical Investigation Plan, Good Clinical Practice (GCP) and in accordance to the national and local laws, regulations, standards, and requirements of the countries/geographies in which the study is conducted. The principles of the Declaration of Helsinki are implemented in this study by means of the informed consent process, Ethics Board approval, study training, clinical trial registration, and risk benefit assessment. The sponsor shall avoid improper influence on, or inducement to, the subject, monitor, any investigator(s) or other parties participating in, or contributing to, the LINQ™ for COPD Study.

This study will be conducted in compliance with international ethical and scientific quality standards, known as good clinical practice (GCP). GCP includes review and approval by an independent Ethics Board before initiating a study, continuing review of an ongoing study by an Ethics Board and obtaining and documenting the freely given informed consent of a subject before initiating the study.

Ultimately, all sites in all geographies will follow and comply with:

- Principles of Declaration of Helsinki
- 21 CFR Part 11: Electronic Records, Electronic Signatures
- 21 CFR Part 54: Financial Disclosure by Clinical Investigators
- The Clinical Trial Agreement
- The procedures described within this CIP
- Local Ethics Board Requirements

*Medtronic Business Restricted*

In addition to the regulatory requirements outlined above, the study will be conducted according to federal, national and local laws, regulations, standards, and requirements of the countries/geographies where the study is being conducted. These include but are not limited to the following:

In the US, the study will be conducted in compliance with:

- 21 CFR Part 50: Protection of Human Subjects
- 21 CFR Part 56: Institutional Review Boards
- 21 CFR Part 803: Medical Device Reporting
- 21 CFR Part 54: Financial Disclosure
- 21 CFR Part 812 Investigational Device Exemptions

The study will not begin until IRB/EC and regulatory authority approvals/notification, as appropriate, are received.

The study will be publicly registered on <http://clinicaltrials.gov> prior to first enrollment in accordance with the 2007 Food and Drug Administration Amendments Act (FDAAA) and Declaration of Helsinki on (PL 110-85, Section 810(a)).

## **16. Study Administration**

### **16.1 Monitoring**

It is the responsibility of Medtronic to ensure proper monitoring of the LINQ™ for COPD clinical study. Trained Medtronic personnel or delegates appointed by Medtronic may perform study monitoring at the study site in order to ensure that the study is conducted in accordance with the CIP, the clinical trial agreement and applicable regulatory and local requirements. Medtronic, or delegates, must therefore be allowed access to the subjects' case histories (clinic and hospital records, and other source data/documentation) upon request as per the informed consent form, Data Protection Authorization (where applicable) and clinical trial agreement. The principal investigator should also be available during monitoring visits.

#### **16.1.1 Monitoring Visits**

Monitoring for the study, including site initiation visits, interim monitoring visits, and closeout visits, will be done in accordance to the study-specific monitoring plan.

Monitoring visits may be conducted periodically to assess site study progress, the investigator's adherence to the CIP, and regulatory compliance, including but not limited to IRB/EC approval and review of the study, maintenance of records and reports, and review of source documents against subject eCRFs. Monitors review site regulatory and study compliance by identifying findings of non-

compliance and communicating those findings to site personnel. Monitors may work with study personnel to determine recommendations for preventative/corrective/effectiveness action(s) recommendations and to identify trends within the study or at a particular site.

Frequency of monitoring visits may be based upon subject enrollment, duration of the study, study compliance, number of adverse events, number of deviations, findings from previous monitoring visits and any suspected inconsistency in data that requires investigation. Regulatory documents may be reviewed at each study center.

